Fig 1. Figure 1 shows comparable cytokine expression of the defining Th2 cytokine/IL-13, the defining Th1 cytokine/IFN gamma, and the Th17/IL-23 cytokines/IL-17A and IL12/23p40 in AA and AD. Lesional psoriasis skin tissues show a significantly higher expression of both IL-17A and IFN gamma, with significantly lower expression of IL-13 as compared with both AA and AD. Significant decreases in mRNA expression of IL-13, and IL12/23p40 are seen after treatment with intralesional corticosteroids, without significant changes in the other cytokines. P value= 0.0002 for the IL-13, and p=0.1 for the IFN gamma lesional vs non-lesional alopecia skin comparisons. JAK3 shows similar activation in AA, AD, and Psoriasis. NL- non lesional skin from scalp of AA patients; L- lesional skin from scalp of AA patients; PTX- post intralesional steroid treatment skin from scalp of AA patients; PS-psoriasis lesional skin; AD- AD lesional skin. N=6 patients for both NL and L, and 4 for PTX.

STUDY DESIGN:

This is a randomized, double-blind, placebo-controlled pilot study of a total of 30 subjects with moderate to severe alopecia areata involving 30-100% of the scalp. We expect 50% of these subjects to have concomitant alopecia areata (AA) and atopic dermatitis (AD).

Subjects with AA alone (15 subjects) will be randomized (2:1) to either receive tralokinumab 300 mg (150 mg/ml) or placebo via subcutaneous injection using 2 pre-filled syringes Q2W for 24 weeks. Subjects with concomitant alopecia areata and atopic dermatitis (15 subjects) will be randomized separately in a 2:1 ratio to receive tralokinumab 300 mg (150 mg/ml) or placebo via subcutaneous injection using 2 pre-filled syringes Q2W for 24 weeks.

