Subjects with concomitant AD will have two additional skin biopsies at Baseline (one from involved skin and one from uninvolved skin), and one additional biopsy at Week 24 or Early Termination visit (in the vicinity of the involved area biopsied at Baseline). An optional biopsy will be performed at Week 12, close to the area that was involved and biopsied at Baseline. All biopsies will be 4.5 mm in diameter.

Our experience in AD¹²⁻¹⁴, and past experience in psoriasis^{15, 16} showed that biomarker studies in skin tissues are critical to the understanding of key pathogenic pathways that are upregulated in each disease and how well they are suppressed with effective treatment. These mechanistic studies coupled with clinical trials are key in the disease to shed light on important disease mechanisms, and to explain which molecules are suppressed by each therapeutic target. We now have data that shows that IL-13 is significantly upregulated in both AD and AA lesions compared to nonlesional skin. It is very important to associate the clinical responses with suppression of this cytokine and related molecules as well as other pathway cytokines in skin tissues. Both the whole genomic profiling and individual molecular and cellular markers are very important in order to understand how well anti-IL-13 will change/suppress AA-associated pathways and compare with those that will be suppressed in AD.

At Baseline, serum will be obtained for DNA (1 PaxGene), RNA (2 PaxGene), and proteomic analysis (2 tubes serum). Studies of RNA and proteomic analysis will further be performed at Weeks 12 and 24. Serum levels of various biomarkers such as interferon gamma, IL-2, IL-12, IL-13, IL-17A, IL-5, IL-10, IL-31 and IL-4 have been shown to be elevated in patients with alopecia areata. Therefore we will assess these Th1, including interferon gamma, Th2, Th17, and Th22 markers in serum before and after tralokinumab treatment. Measurements of serum anti-drug antibodies (ADA) including neutralizing antibodies (nAb), as well as serum tralokinumab levels will be performed at Baseline, Weeks 4, 12, and 24 and at Early Termination visit if it occurs prior to Week 24.

Mechanistic blood analyses including RNA, DNA, and proteomic analysis, as well as ADA and serum drug levels will be conducted collaboratively with Medimmune/Astra Zeneca.

INCLUSION CRITERIA:

1. Male or female, aged from 18 to 75 years, inclusively at the time of signing the informed consent document.

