The Principal Investigator will provide safety data to an independent Data and Safety Monitoring Board every 12 months. This DSMB will be comprised of board certified dermatologists who are not directly related to this study. The DSMB will review the data and provide a report of their findings to the Principal Investigator.

EARLY TERMINATION

Any individual whose health or well being may be threatened by continuation in this study will be discontinued by the investigator.

If a female subject becomes pregnant at anytime during the study, she will be discontinued immediately. She will be asked to provide the investigator with medical updates throughout her pregnancy and on the final outcome of the pregnancy.

Any subject who chooses to discontinue the study, or is discontinued from the study by the investigator will be asked to return for a final Early Termination visit for the procedures listed in the Schedule of Events table.

Considering there is no current treatment that is very effective in treating alopecia areata, these subjects are highly motivated to participate in any study that may provide a treatment option. Thus, we have accounted for a 10% drop out rate, and plan to enroll 30 subjects in order to have 27 subjects complete the study.

INVESTIGATIONAL DRUG SUPPLY

In this double-blind study, the investigator will supply tralokinumab (formulated at 150 mg/ml in an isotonic sodium acetate buffer at pH 5.5 in accessorized prefilled syringes for subcutaneous injection) 300 mg for up to 20 subjects and placebo for up to 10 subjects. The tralokinumab and placebo will be provided by MedImmune as 150 mg tralokinumab (and matching placebo) prefilled syringes. Both the 150 mg tralokinumab and the matching placebo prefilled syringes will be of the same quality and identical in size and shape. All study medication will be stored in a secure cool area between 2-8°C. Study drug will be administered to subjects at each visit, and any unused study drug will be kept at the study site. The number of missed doses will be documented for each subject. The investigative site will account for all study drug dispensed and stored during the study.

EFFICACY EVALUATIONS

The following efficacy parameters will be obtained at the previously specified visits:

1. Investigator evaluation of alopecia on the scalp (efficacy of the drug) using the following tools:

Severity Alopecia Tool (SALT)⁵ score:

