Prior to beginning this study, approval for all study related documents (protocol, consent form, advertising) would be obtained from the Icahn School of Medicine at Mount Sinai Program for the Protection of Human Subjects (Institutional Review Board), [name].

DATA ANALYSES:

This is an exploratory study therefore sample size has been kept relatively low. Data collected from this study will be used to obtain estimates of differences and variability, of the change in treatment for IL-13. If the variability of the Post vs Pre differences are of the magnitude of the LS vs NL differences observed in preliminary data (SE=0.46) then the size of the confidence interval in differences could be observed in this study would be 0.58. As for the secondary outcome, the spontaneous regrowth rate in alopecia areata is 4%. To demonstrate efficacy of the study drug, a response rate of at least 50% is required. To be statistically significant, we would require a minimum of 10 subjects in the study, with an expected response rate of 0 or 1 subject in the placebo group.

MECHANISTIC STUDIES DATA ANALYSES:

For the comparisons of expression levels of lesional, and non-lesional AA skin, we will use RT-PCR, and gene-arrays. RT-PCR values will be normalized to the housekeeping gene hARP (validated in all our AD studies) and log2-transformed prior to analysis. Microarray data will be preprocessed using standard pipeline (exhaustively used by our group in a large number of studies) and log-2 transformed expressions. Adjustments by batch effect and clinical variables will be carried out if needed using ComBat. Mixed effect model on R's *limma* framework will be used and p-values for the moderated t-tests and paired-t-test will be adjusted by Benjamini-Hochberg procedure.

Extensive bioinformatics tools will be employed to gain insights on the results and test hypotheses that are generated in the "data mining stage". This will include (but is not be limited to) pathway and gene-set enrichment analyses using Ingenuity software, GSEA, the R package GSVA (Gene Set Variation Analysis) and other in-house codes produced by our group.

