To define cellular and molecular biomarkers of AA in skin biopsies, biomarkers will be divided into those that show significant group differences and those that do not. Multiple regression models will be used to determine the best set of biomarkers that predict disease activity and response. Similar approaches will be carried out for blood analyses.

Gene expression changes in Th2/IL-13, "T22"/IL-22, S100A7 and S100A8, Th1/IFN-gamma, and Th17/IL-17A will be jointly correlated with clinical responses by multivariate analysis using multivariate u-statistics and R package muStat, as we have previously reported.

DATA AND SAFETY MONITORING PLAN

Since this is a phase II study, with few subjects and minimal risks, this project will be monitored by the principal investigator, sub-investigators, and independent DSMB. Both the principal investigator will provide safety data to an independent Data and Safety Monitoring Board every 12 months. This DSMB will be comprised of dermatologists who are not directly related to this study. The DSMB will review all the safety data and provide a report of their findings to the Principal Investigator.

All non-serious events will be reported to the IRB and FDA (on behalf of the IND) on a yearly basis. All serious events will be reported to the IRB and FDA within 24 hours of becoming aware of the event.

Schedule of Events

Formatted: Left: 0.75", Right: 0.75", Top: 1", Bottom: 1", Width: 11", Height: 8.5"

Procedures	Screening (Day -28 to Day -1)	Base-line Day 0	Weeks 2, 6	Week 4	Week 8	Week 10	Week 12	Weeks 14 and 18	Weeks 16 and 20	Week 22	Week 24	Week 32	Week 40	Early Term Visit
Informed consent	X													
Inclusion/exclusion criteria	X	X												
Past Medical History (including demographic data and age on onset)	X													
ECG	X											X		X ⁶
Limited Physical Examination	X						X				X	X	X	X
Vital Signs ¹	X	X	X	X	X	X	X	X	X	X	X			
Chemistry and hematology	X	X		X			X				X	X		X ⁶
PPD or Quantiferon Gold	X													
HIV screening	X													
HBsAg, Anti-HBc antibody	X													
Pregnancy test ²	X	X	X	X	X	X	X	X	X	X				X ⁷
Assessment of Regrowth Pattern	X	X	X	X	X	X	X		X		X	X	X	X
SALT assessment	X	X	X	X	X	X	X		X		X	X	X	X
Subject Questionnaires AASIS and AA-QoL		X		X	X		X		X		X	X	X	X

Procedures	Screen-ing (Day -28 to Day -1)	Base-line Day 0	Weeks 2, 6	Week 4	Week 8	Week 10	Week 12	Weeks 14 and 18	Weeks 16 and 20	Week 22	Week 24	Week 32	Week 40	Early Term Visit
SCORAD, EASI, IGA ³		X		X	X		X		X		X	X	X	X

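### The planned marker–response correlation names no treatment arm or analysis population; if the arms are pooled and tralokinumab affects both marker and regrowth, it can show links absent within arm

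*Combined protocol and SAP*

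**What the plan says.** The relevant text is in the combined protocol and SAP, under MECHANISTIC STUDIES DATA ANALYSES. Expression changes in the Th2/IL-13, T22/IL-22, S100A7/S100A8, Th1 and Th17 markers "will be jointly correlated with clinical responses by multivariate analysis using multivariate u-statistics and R package muStat". For detail it points to the group's own published work. The paragraph before it plans a companion model: "Multiple regression models will be used to determine the best set of biomarkers that predict disease activity and response". Neither sentence says whether the two arms are pooled, whether only tralokinumab subjects are used, or whether treatment or the AA / AA+AD group enters as a factor.

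The only adjustment named in the section concerns preprocessing of the expression data: "Adjustments by batch effect and clinical variables will be carried out if needed using ComBat". Treatment arm is not mentioned there.

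The purpose is stated under STUDY DESIGN: "It is very important to associate the clinical responses with suppression of this cytokine and related molecules". The same section sets up a placebo-controlled comparison with 2:1 allocation, made separately in the AA-alone and AA+AD groups.

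**The concern.** A correlation across two randomised arms mixes two sources of association. One is within arm: whether patients whose marker falls more also regrow more hair. The other is between arms: the treated group may differ from placebo on both variables because of the drug. If tralokinumab moves both, the second source gives a positive correlation even when the first is zero.

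The question the protocol wants answered is whether clinical response goes with marker suppression. A pooled correlation cannot separate that from the plain statement that the drug changed both. The problem arises in the outcome the study hopes for, a clinically active drug, which is when the correlation is most likely to be cited as evidence of mechanism. Several marker groups are examined. One that the drug changes incidentally could therefore be reported as tied to regrowth.

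**Working it through.** The plan gives no figure for this analysis, so there is none to reproduce. The inputs it rests on agree with one another.

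**Inputs from the document**
- Allocation (STUDY DESIGN): "will be randomized separately in a 2:1 ratio to receive tralokinumab 300 mg", and likewise 2:1 for AA alone.
- Arm sizes (INVESTIGATIONAL DRUG SUPPLY): "300 mg for up to 20 subjects and placebo for up to 10 subjects". Check: 30 × 2/3 = 20 and 30 × 1/3 = 10.
- Completers (EARLY TERMINATION): "we have accounted for a 10% drop out rate, and plan to enroll 30 subjects in order to have 27 subjects complete the study". Check: 30 × 0.9 = 27.
- Response rates (DATA ANALYSES): 4% spontaneous regrowth, 50% required on drug.

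**Assumptions, not in the document**
- Equal dropout by arm, giving 18 v 9.
- Two-sided 5% test; the plan sets no level for this correlation.
- Drug effect on the marker, dM, of 1 to 2 within-arm SD.
- For a continuous response, drug effect dY of 0 to 2 SD.
- No marker–response association within either arm.

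**Induced correlation, continuous response.** With p = 2/3, q = 1/3 and pq = 2/9 = 0.222:

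r = pq·dM·dY / √[(1 + pq·dM²)(1 + pq·dY²)]

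- dM = dY = 1: 0.222 / 1.222 = 0.18
- dM = dY = 1.5: 0.500 / 1.500 = 0.33
- dM = dY = 2: 0.889 / 1.889 = 0.47
- dY = 0, any dM: the numerator is 0, so r = 0

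**Induced correlation, binary response at 50% v 4%.** The overall rate is (2/3)(0.50) + (1/3)(0.04) = 0.347, with variance 0.347 × 0.653 = 0.226. Then:

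r = 0.222·dM·0.46 / √[(1 + 0.222·dM²)·0.226]

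This gives 0.19, 0.26 and 0.31 for dM = 1, 1.5 and 2.

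**Simulated false-link rate.** 40,000 trials per setting, one marker, 18 v 9:

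| Setting | Pooled Pearson, p<0.05 | Linear model with arm term |
|---|---|---|
| 50% v 4% response, dM = 1 / 1.5 / 2 | 16% / 26% / 36% | 5% / 5% / 5% |
| Continuous, dM = dY = 1 / 1.5 / 2 | 15% / 43% / 78% | 5% / 5% / 5% |
| Continuous, dM = 1, dY = 0.5 | 8% | 5% |
| Continuous, dY = 0, dM = 1 to 2 | 5% | 5% |
| 4% response in both arms, dM = 1 to 2 | 3.0% to 3.4% | 3.1% to 3.4% |

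Repeat runs moved these by about one percentage point. Spearman correlation gave nearly the same pooled rates wherever the drug affects regrowth (for example 16%, 27% and 36% in the first row).

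**Power cost of the arm term.** Suppose instead that the link is real: slope 0.5 of response on marker, unit SDs, 18 v 9. The test is significant this often:

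| Marker shift | Pooled | Arm-adjusted | Tralokinumab arm only (n = 18) |
|---|---|---|---|
| 1 SD | 75% | 65% | 48% |
| 2 SD | 90% | 65% to 66% | 48% |

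**The case against.** Four points can be made for the plan as it stands.

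**Pooling is not stated.** The text is silent on population. Other sentences under STUDY DESIGN speak of how far anti-IL-13 suppresses pathways and of serum markers before and after tralokinumab, which would fit an analysis of treated subjects only. Such an analysis has no arm confounding. This stands: pooling is the natural reading of an unqualified correlation, but it remains an inference. The silence still needs closing, because it permits both versions.

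**A link is not inevitable.** A reader might infer that any marker the drug moves will appear tied to regrowth. The document and the arithmetic do not support that. Whether the drug affects regrowth is the hypothesis under test. If it does not, the pooled rate is not inflated. Even at the plan's 50% v 4% rates, most simulated trials show no significant false link.

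**The planned method was not the one simulated.** The plan describes a joint multivariate u-statistic; the check uses one marker at a time. The effect sizes are assumed, and 78% needs a 2 SD shift in both variables. The rates are therefore indicative. The mechanism does not depend on the choice of statistic: the rank-based version behaves the same way.

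**The study is exploratory.** This correlation is not among the listed endpoints and no decision rule uses it. An arm term also removes part of the signal if marker suppression is the true pathway. Both are correct and limit the weight of the point. They do not make a pooled correlation evidence of a within-arm link. In an exploratory study the estimates are the product, and here the mean pooled r is about 0.2 to 0.5 in the 50% v 4% and equal-shift settings, when the within-arm value is zero.

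**Conclusion.** The concern holds in conditional form. The plan does not state whether arms are pooled or how arm is handled. If they are pooled, and tralokinumab affects both the marker and regrowth, the correlation partly restates the treatment effect and can show a link that is absent within arm.

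Under the assumptions listed, the false-link rate is about 16% to 37% at the plan's response rates and about 15% to 78% with an equally shifted continuous response, against about 5% once arm is adjusted for. Smaller effects give less (8% at dM = 1, dY = 0.5). This is an inexpensive improvement to an exploratory analysis. It does not touch the primary comparison.

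**What to change.** State the analysis population for the marker–response correlation. Make the reported association one stratified by treatment arm, either a stratified u-statistic or a partial correlation adjusting for arm. Show the tralokinumab-arm estimate beside it. If a pooled correlation is also given, label it descriptive. State in the same way how arm is handled in the companion regression for response.

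Adjustment for the AA / AA+AD group can be left optional: 15 subjects per group at 2:1 leaves about 5 placebo subjects in each before dropout.

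The cost is a sentence or two of text, a stratified version of the statistic, and the loss of power shown above. Reporting the pooled estimate alongside means no information is lost. An arm-adjusted association is still not proof of mediation and should not be described as such.

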- Electrocardiogram (ECG) was added to the assessments performed during the screening visit.
- Serum tralokinumab levels were added to the Baseline visit as recommended by the FDA.

Page 6 & 7:

- Serum tralokinumab levels and antidrug antibody (ADA) measurements were added to the Week 4 and Week 12 visits as recommended by the FDA.
- Serum tralokinumab levels were added to the Week 24 visit as recommended by the FDA.
- Blood tests for chemistry and hematology were changed from the Week 22 visit to the Week 24 visit.
- Two paragraphs explaining the procedures for Early Termination Visits were added.

Page 8:

- We clarified the language used regarding the location where the biopsies will be performed.
- In the last paragraph, we added the information regarding the serum drug levels that were suggested by the FDA.

Page 9:

- Inclusion Criteria: We revised the language for contraception to be used by women of childbearing potential.

Page 15 and 20:

- The Principal Investigator will provide safety data to an independent Data and Safety Monitoring Board every 12 months instead of every 6 months.

Page 16:

- We removed the paragraph listing the procedures to be performed at the Early Termination Visit, as this has been added under study design.

Pages 21-23:

- the table on pages 21 through 23 was updated to be consistent with the protocol, and the title of the table was changed from “flow chart” to “Schedule of Events”.
